## 7.2 Statistical Analysis

Tabulations overall, and by treatment group, will be produced for appropriate demographic, baseline, efficacy, and safety parameters, with number and percentages reported for categorical variables and the mean, median, standard deviation, and range for continuous variables. All analyses will be performed at an  $\alpha=0.05$  level using SAS v.4.

Efficacy analyses will be performed in an intention-to-treat (ITT) population consisting of all patients randomized. The difference in ordinal scale improvement rates between treatment arms will be calculated with a 95% confidence interval and formally compared using Fisher's Exact Test. For secondary analysis of the primary endpoint, logistic models individually adjusted for age, diabetes, chronic lung disease/moderate or severe asthma, immunocompromise, liver disease, heart disease/hypertension, smoking and obesity (BMI  $> 40$ ), residence in long-term care facility, will also be examined with odds ratios and 95% confidence intervals reported.

The analysis of secondary time to event endpoints including survival at 30 days, duration of hospitalization, duration of ventilation and ventilator free days, will be compared between treatment arms based on a log-rank test. The median will be estimated with a 95% CI for each treatment arm using the Kaplan-Meier method. Cox proportional Hazards models adjusted individually for age, diabetes, chronic lung disease/moderate or severe asthma, immunocompromise, liver disease, heart disease/hypertension, smoking and obesity (BMI  $> 40$ ), residence in long-term care facility, will also be examined with odds ratios and 95% confidence intervals reported. Changes in inflammatory markers and in oxygenation or  $\text{paO}_2/\text{FIO}_2$  ratio, based on available recorded measurements, will be compared between treatment arms using a two sample t-test, or a Wilcoxon Rank Sum test, as appropriate. Incidence of grade 3 or 4 AEs and serious AEs will be compared using Fisher's Exact test.

Additional safety analyses will be based on the reported adverse events and other clinical information. Safety analyses will be performed in the all-treated (AT) population, consisting of all patients who took at least one dose of study treatment. The safety and tolerability of Etoposide will be evaluated by means of drug-related AE reports, physical examinations, and laboratory safety evaluations and compared between groups using Fisher's exact test. The first 10 patients allocated to the Etoposide group in the ventilated cohort will be evaluated for safety endpoints prior to initiating enrollment in the non-ventilated group.

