## 7. STATISTICAL CONSIDERATIONS

### 7.1 Sample Size Considerations

This study will be performed with two cohorts 1) severe COVID-19 infection and 2) moderate COVID-19 infection (as defined in inclusion criteria).

The effect of the intervention will be evaluated in each cohort separately. A total of 32 patients will be enrolled in each cohort with a 3:1 allocation ratio (24 Etoposide and 8 control per cohort). Assuming a 30% response rate in the control group for the primary outcome of a 2 point improvement in respiratory status on an 8 point scale at Day 14, we can detect a 50% increase in response in the Etoposide group (80% response rate in the Etoposide group) with a 2-sided  $\alpha$  of 0.05 and 80% power. While this study is not powered to detect a statistically significant difference in outcome, it will provide initial evidence of efficacy if improvement in response is observed.

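### Fisher's exact test at 24 vs 8 is valid but conservative: power is 67.9% rather than the stated 80%, Boschloo's test would give 72.9%, and the 95% interval beside it has no named method

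*Combined protocol and SAP*

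**What the plan says.** Section 7.1 fixes the design of each cohort, and the cohorts are analysed separately: "A total of 32 patients will be enrolled in each cohort with a 3:1 allocation ratio (24 Etoposide and 8 control per cohort"). The power statement has two parts. The first is "Assuming a 30% response rate in the control group for the primary outcome", a 2-point improvement at Day 14. The second is "we can detect a 50% increase in response in the Etoposide group (80% response rate in the Etoposide group"), at two-sided alpha 0.05 and 80% power. The test behind that figure is not named. The same paragraph then adds that the study is not powered for statistical significance and will offer initial evidence of efficacy.

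Section 7.2 sets the primary analysis in all randomized patients: "The difference in ordinal scale improvement rates between treatment arms will be calculated with a 95% confidence interval and formally compared using" Fisher's exact test. The level is given by "All analyses will be performed at an $\alpha=0.05$ level using SAS v.4". No method is named for the interval, and nothing says which result governs if interval and test disagree.

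**The concern.** With only 8 controls the possible results are few and coarse, so the choice of exact test and of interval has a visible effect. Two things are at stake.

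- **Efficiency.** A conditional exact test can fall well short of its nominal level in a table this small. Power is then given up on the primary comparison, in a cohort of 32 that has little to spare.
- **A coherent primary result.** An interval chosen after the fact, or by software default, may be too narrow. It may also exclude zero beside a non-significant p-value. Because 7.1 expects the observed improvement to serve as initial evidence of efficacy, the interval is likely to carry much of the interpretation in this open-label study.

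**Working it through.** **Inputs.** From 7.1: 24 etoposide and 8 control, response 80% vs 30%, two-sided alpha 0.05. From 7.2: Fisher's exact test, 95% CI for the difference, all randomized patients. No dropout is assumed.

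**1. Reproducing the stated 80%.** The unpooled normal approximation comes closest:

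- SE = √(0.8×0.2/24 + 0.3×0.7/8) = √(0.00667 + 0.02625) = 0.1814
- Power = Φ(0.5/0.1814 − 1.960) = Φ(2.756 − 1.960) = 78.7%
- Controls needed for 80% = (1.960 + 0.842)² × (0.21 + 0.16/3)/0.25 = 8.27, so a total of 4 × 8.27 = 33.1 against the planned 32

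The pooled version gives 75.5%. The stated figure therefore matches a large-sample z-test, not the test named in 7.2.

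**2. Exact size and power.** There are 25 × 9 = 225 possible tables. For any rejection rule,

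P(reject) = Σₓ Σᵧ Bin(x; 24, p_E) × Bin(y; 8, p_C) × 1{table (x, y) rejected}.

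Size is the maximum of this over a common rate p_E = p_C. Boschloo's test uses Fisher's p-value as its statistic and takes the largest cut-off whose maximum size stays at or below 5%. Here that cut-off is 0.072. The next attainable one, 0.081, has a maximum size of 5.14%.

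| | Fisher | Boschloo |
|---|---|---|
| Tables rejected (of 225) | 90 | 98 |
| Maximum type I error | 3.1% | 4.3% |
| Type I error at 30% vs 30% | 2.8% | 4.2% |
| Power, 80% vs 30% | 67.9% | 72.9% |
| Power, 75% vs 30% | 55.7% | 60.4% |
| Power, 70% vs 30% | 44.2% | 48.1% |

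Boschloo's region contains Fisher's plus 8 tables, so its power cannot be lower anywhere. The gain at the design point is 72.9 − 67.9 = 5.0 points. At 3:1, Fisher's test first reaches 80% power at 44 per cohort (33 vs 11, 81.7%).

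**3. The interval, if Wald were used.** The interval is d ± 1.960 × √(p̂_E(1−p̂_E)/24 + p̂_C(1−p̂_C)/8), evaluated on the same 225 tables.

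| True rates | Wald coverage | Wald excludes zero, Fisher p > 0.05 |
|---|---|---|
| 80% vs 30% | 90.3% | 7.3% |
| 70% vs 30% | 90.4% | 12.8% |
| 30% vs 30% | 90.4% | 6.9% |

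The conflict arises in 24 of the 225 tables. For example, 19/24 vs 3/8 gives Fisher p = 0.072 and a Wald interval of 0.044 to 0.789. With no effect at a 30% rate, the Wald interval excludes zero in 9.6% of trials.

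**4. Does a better interval alone cure the conflict?** No. A Miettinen-Nurminen score interval covers 95.2% at 80% vs 30%. It still excludes zero without Fisher rejection in 10 of 225 tables, with probability 6.6% at 80% vs 30%. Paired with Boschloo's test it disagrees in 2 tables (16/24 vs 2/8 and its mirror image 8/24 vs 6/8). That has probability 1.6% at 80% vs 30% and 4.8% at 70% vs 30%.

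**The case against.** Fisher's test is valid, pre-specified and widely understood. The gain from replacing it comes from 8 tables, is 3.8 to 5.0 points at the rates checked, and leaves power below 80%. Section 7.1 itself disclaims power for significance in this small phase II study. All of that stands, and it makes this a question of efficiency, not of validity. It does not dispose of the point: 7.1 still states 80% power, 7.2 still prescribes a formal test at 0.05, and a test that controls the error at 5% with more power is available for the same patients.

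Two stronger readings are tempting, and the documents do not support them.

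- **That the trial will report a Wald interval with about 90% coverage.** Wald is not mentioned anywhere. That software might supply it by default is an assumption. The documented gap is that the method is left open, so a Wald interval would comply with the plan.
- **That any conflict between interval and test would be the fault of a poor interval.** At the design point a score interval conflicts with Fisher's test almost as often as Wald does (6.6% against 7.3%). Most of the conflict there comes from Fisher's conservatism, so replacing the interval alone would not be enough.

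The guarantee of never being less powerful than Fisher's test belongs to Boschloo's test by construction. It is not a general property of unconditional tests such as Barnard's, although Barnard's test also gives 72.9% at 80% vs 30%.

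**Conclusion.** The point holds as lost efficiency, a power figure that does not belong to the planned test, and an under-specified interval. Fisher's test at 24 vs 8 has a maximum type I error of 3.1% and 67.9% power at the plan's own rates, 12.1 points below the stated 80%. Boschloo's test recovers 5.0 of those points within the 5% level. Neither test delivers 80%.

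A reader might infer that the primary test is invalid or inflates false positives. It does neither; it errs on the cautious side.

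The size and power figures rest on 24 and 8 analysed patients, independent binomial outcomes and the response rates in 7.1. The coverage and conflict figures for Wald rest also on the assumption that Wald would be chosen.

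**What to change.** In 7.2:

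- Name Boschloo's exact unconditional test, two-sided at 0.05, as the primary comparison in each cohort, with Fisher's p-value as a sensitivity result.
- Report the 95% CI for the difference obtained by inverting that test. If a Miettinen-Nurminen interval is preferred, state that the test governs in the 2 of 225 tables where they disagree.
- State that a Wald interval will not be used.

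In 7.1, name the test behind the power figure and restate it: about 73% at 80% vs 30% for Boschloo's test, or about 68% if Fisher's is kept.

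The cost is a few sentences and no extra patients. The downsides are a less familiar test and a stated power below 80%. The change should be made before outcomes by arm are seen; the documents do not show whether that is still possible. If it is not, keep Fisher's test as primary, name the interval method and which result governs, and correct the power figure.

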### **3.3 Exclusion Criteria**

- Pregnancy or breastfeeding
- History of severe hypersensitivity to etoposide products
- Absolute neutrophil count (ANC) < 1000 cells/mm^3
- Platelet count <50,000/mm^3
- Bilirubin > 3.0 mg/dL
- Aspartate OR alanine aminotransferase > 5.0 x ULN
- Creatinine Clearance < 15 mL/min (calculated by Cockcroft and Gault formula)
- Requiring continuous renal replacement therapy
- Requiring > 1 vasopressor medications
- Requiring extracorporeal membrane oxygenation (ECMO)
- Other active, life-threatening infections
- Anti-cytokine treatment (including anakinra or IL6 antibodies eg tocilizumab, sarilumab) administration within three half-lives of the medication used
- Hydroxychloroquine, colchicine, azithromycin, doxycycline—if administered for COVID infection—must be discontinued for at least 24 hrs prior to randomization.
- Has a history or current evidence of any condition, therapy or laboratory abnormality that might confound the results of the study, interfere with subject participation, or is not in the best interest of the patient to participate, in the opinion of the investigator.
- Inability to consent and no legally authorized representative
- Poorly controlled HIV infection (CD4 count <100 cells/mm^3)

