## 6. STUDY PROCEDURES & CALENDAR

REQUIRED STUDIES	Screening	Day 1, Day 4 and Day 7 Σ#	Prior to discharge	Day 30*
PHYSICAL				
History & Physical Exam	X	X	X	X
Height, Weight, Body Mass Index, and Body Surface Area	X			
Vital Signs	X	X	X	X
Toxicity Notation	X	X	X	X
Respiratory Status on 8 point scale ^	X	X	X	X
HISTORY				
Concomitant medicines (including COVID therapies, ie hydroxychloroquine, tocilizumab, anakinra) with date of initiation	X			
Smoking status	X			
Comorbidities	X			
Symptoms, including date of symptom onset	X			
LABORATORY				
Beta HCG (for women of childbearing potential)	X			
CBC with Differential +	X	X	X	X
Comprehensive metabolic panel +	X	X	X	X
Lactate Dehydrogenase	X	X	X	X
D-dimer	X	X	X	X
Ferritin	X	X	X	X
C-reactive protein	X	X	X	X
PaO 2 /FIO 2 (P/F) ratio (cohort 2 only)	X	X	X	X
INR (if on warfarin) Ω	X			
ADDITIONAL TESTING				
Electrocardiogram (ECG)	X			

# For subjects randomized to treatment, the data for Day 1 and Day 4 will be collected prior to the etoposide dose (within 24 hours).

\*Information to be obtained as feasible, if patient has been discharged attempts will be made to obtain the information from the patient's primary care provider. If such results are not available, participant will be contacted by the research nurse to assess toxicities.

^ Mortality assessment (included on the 8 point scale) will also be recorded at Day 14 and 60, in addition to Day 30 mentioned above

+ CBC and comprehensive metabolic panel will be measured at least twice weekly during hospitalization. These tests will also be obtained pre-dose 8, 11, 18, and 25 for those patients who require additional etoposide dosing as described above (Section 4.3 and 5.3)

Ω INR to be repeated at least twice weekly for patients on warfarin

Σ Day 1 of treatment for patients randomized to standard of care (SOC) will be considered the day of randomization

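### The adjusted analyses of the primary endpoint omit the baseline 8-point category, so a chance imbalance in starting level within a cohort (24 vs 8) would go unadjusted

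*Combined protocol and SAP*

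**What the plan says.** Section 7.2 compares improvement rates between arms with an unadjusted Fisher's exact test and a 95% confidence interval for the difference, in all randomized patients. As a secondary analysis of the same endpoint it plans "logistic models individually adjusted for age, diabetes, chronic lung disease/moderate or severe asthma, immunocompromise, liver disease, heart disease/hypertension, smoking and obesity", with residence in long-term care as a further covariate. Each covariate gets its own model. No other section adds the starting level.

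The starting level is available. The calendar in section 6 has a row for "Respiratory Status on 8 point scale", marked at Screening and at Day 1. In the etoposide arm the Day 1 value is taken before the dose.

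Section 4.3 randomizes 3:1 in blocks of 4 within each cohort and names no other stratification factor. Section 7.1 evaluates each cohort separately, with 24 etoposide and 8 control patients.

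**The concern.** The endpoint is a change from baseline, so the starting level is built into it. Eligibility (sections 3.2 and 3.3) and the scale (section 8.2) together leave two starting levels in each cohort:

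| Cohort | Start | Minimum state that counts as a response |
|---|---|---|
| 1 | 7 | 5: non-invasive ventilation or high-flow oxygen |
| 1 | 6 | 4: oxygen by mask or prongs |
| 2 | 5 | 3: in hospital, off oxygen |
| 2 | 4 | 2: discharged |

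Level 7 is open in cohort 1 because the relevant exclusion is "Requiring > 1 vasopressor medications". A ventilated patient on a single vasopressor at the scale's dose threshold can therefore enter.

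Two patients in the same cohort can thus need different events to count as responders. If the arms differ by chance in their mix of starting levels, part of the crude difference reflects that mix. None of the listed covariates measures it. Section 7.1 says the trial is not powered for significance and will offer initial evidence of efficacy if improvement is seen, so interpretation will rest on the observed difference.

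**Working it through.** **1. The plan's own figure.** Section 7.1 assumes 30% vs 80% response with 24 and 8 patients, two-sided alpha 0.05, and states 80% power. With an unpooled z-test, SE = sqrt(0.3×0.7/8 + 0.8×0.2/24) = 0.181 and power = Φ(0.50/0.181 − 1.96) = 78.7%, so the figure is essentially reproduced. Enumerating the planned two-sided Fisher test gives 67.9%. That gap is a separate matter; 67.9% serves here only as the reference for step 4.

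**2. Chance of imbalance.** Let p be the share of a cohort at one of its two levels. The documents do not give p, so the values are assumptions. The SD of the arm difference in that share is sqrt(p(1−p)(1/24 + 1/8)). The probability of an absolute difference of 20 points or more, in either direction, is summed exactly over two independent binomials:

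| p | SD (points) | P(imbalance ≥ 20 points) |
|---|---|---|
| 5% | 8.9 | 4% |
| 10% | 12.2 | 12% |
| 20% | 16.3 | 25% |
| 30% | 18.7 | 32% |
| 40% | 20.0 | 35% |
| 50% | 20.4 | 36% |

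Fixing the number at one level instead (hypergeometric, ignoring blocking) gives 15%, 38%, 42% and 22% for 8, 10, 13 and 16 of 32 patients. The values jump because one control patient is 1/8 = 12.5 points of that arm.

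**3. Effect on the observed difference.** With no treatment effect, the shift equals the imbalance times the gap in response between levels. For an assumed gap of 30 points this is 0.20 × 0.30 = 0.06, or 6 points. For gaps of 20 and 40 points it is 4 and 8 points.

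A simulation gives a wider picture: 20,000 trials per setting, blocks of 4 at 3:1, 8, 13 or 16 of 32 patients at the harder level, overall control response 30%, and an assumed odds ratio of 0.37 or 0.11 for harder vs easier level. Controls had at least 20 points more patients at the harder level in 8% to 15% of trials. In those trials the mean crude difference was 6 to 15 points when the true difference was 0, and 56 to 63 points when it was 50.

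**4. Effect of adjusting.** In the same simulation, an exact test stratified on starting level was set against Fisher's test:

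| Odds ratio, harder vs easier | Fisher power | Stratified power |
|---|---|---|
| 0.37 | 67.4-67.7% | 66.5-66.9% |
| 0.11 | 67.1-67.3% | 71.6-73.0% |

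Type I error was below 3% for both tests in every setting.

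**The case against.** The strongest reply is that little depends on this. Fisher's test on all randomized patients needs no covariates to be valid, and the gap lies in a supportive analysis. Separate randomization and analysis by cohort already remove the largest severity contrast, 4/5 versus 6/7. Section 7.2 also tabulates baseline parameters by arm, so an imbalance could at least be seen. A 6-point shift is small beside a 50-point target and is about half of one control patient's weight. All of this stands and limits the weight of the point. But a tabulated imbalance is not an adjusted estimate, and none of this explains why the listed covariates are modelled while the starting level is not.

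A second reply concerns cohort 1. Continuous renal replacement, ECMO and more than one vasopressor are all excluded, and a single vasopressor below the scale's threshold leaves a patient at level 6. The share at level 7 could be small, which is why the table in step 2 goes down to 5%. Cohort 2, where the 4-versus-5 contrast is clearer, opens only if permitted.

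A reader might infer more than the documents support:
- **That imbalance is likely.** Even at a 50% share, the chance of 20 points or more is 36% in either direction.
- **That starting level is the strongest predictor of response.** No response rates by level are given, nor which level is harder.
- **That the same covariate belongs in the Cox models.** The argument rests on what a 2-point gain requires and does not carry over to survival or duration endpoints.

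**Conclusion.** The omission is real: a variable that defines the endpoint, and is already recorded, is missing from the adjusted analyses, and neither the randomization nor any planned model compensates within a cohort. The consequence is conditional bias and some loss of precision in reading the result. It is not a type I error problem, and the primary test does not need replacing.

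The size depends on two quantities that the documents do not give. The chance of an imbalance of 20 points or more runs from about 4% to 36% as the assumed share at one level goes from 5% to 50%. With an assumed 30-point gap in response between levels, such an imbalance at 20 points moves the observed difference by about 6 points. The direction cannot be settled from the documents. The omission itself is certain; its practical effect is modest and uncertain. The change is worth making because it is nearly free.

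**What to change.** Keep Fisher's exact test as the primary comparison. In section 7.2, prespecify within each cohort one secondary model of the primary endpoint containing treatment and baseline 8-point category, fitted by a small-sample method such as Firth-penalised or exact logistic regression because there are only 8 controls. Define baseline as the last score before treatment or randomization, since the plan does not say whether Screening or Day 1 applies, and use the same score to calculate the 2-point gain. Keep the listed single-covariate models as sensitivity analyses and leave the Cox models as they are.

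The cost is a few lines of text and one extra model per cohort, with no new data. In the simulation, where an exact stratified test stood in for the model, adjustment lost about 1 point of power when the category was weakly prognostic and gained about 4 to 6 points when it was strongly prognostic. If one level is rare, it may contain few or no controls and add little information, and the report should say so. The wording should be settled before outcomes by arm are examined: the trial is open-label and the investigator assesses the primary endpoint (section 10.1), so a covariate added later would be post hoc.

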## **2.5 Secondary Objectives**

- Overall Survival at 30 days is a key secondary endpoint.
- Improvement in inflammatory markers associated with cytokine storm (Ferritin, C-Reactive Protein (CRP), d-dimer, white blood cell count)
- Cumulative incidence of grade 3 and 4 adverse events during hospitalization
- Cumulative incidence of serious adverse events during hospitalization
- Duration of hospitalization
- Duration of ventilation
- Ventilator free days (reintubations or death within 28 days will result in zero ascribed time off ventilator prior to reintubation)
- Improvement in oxygenation or paO2/FIO2 ratio

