## **4. INVESTIGATIONAL PLAN**

### **4.1 Overall Design**

Open-label, randomized Phase II study of etoposide administered intravenously at a dose of 150 mg/m^2 once daily on Days 1 and 4 for a total of two doses to inpatient patients with moderate and severe COVID-19 who have consented to treatment on this clinical trial. Dose reductions will be performed as outlined in Section 5.

This study includes a screening period, a treatment period, and a follow-up period for adverse events that will include the remainder of hospitalization, with additional assessments at days 30 and 60 as outlined in the study calendar (Section 6). After obtaining informed consent, the patients randomized to etoposide will begin treatment with the study drug. Subjects randomized to control will receive standard of care treatment. No placebo will be used. Subjects will be monitored for adverse events and to evaluate study outcomes. Patients removed from the study due to any unacceptable adverse events will also be followed until time of death or hospital discharge.

For patients randomized to standard of care, day 1 will be considered day of randomization. These patients will be followed to record the outcome of all primary and secondary objectives until time of death or hospital discharge, whichever occurs earlier.

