## 8.2 Response Definitions

8-Point Ordinal Scale:

- 8 - Death;
- 7 - Ventilation in addition to extracorporeal membrane oxygen (ECMO), continuous renal replacement therapy (CRRT), or need for vasopressors (dopamine  $\geq 5$   $\mu$ g/kg/min OR epinephrine  $\geq 0.1$   $\mu$ g/kg/min OR norepinephrine  $\geq 0.1$   $\mu$ g/kg/min);
- 6 - Intubation and mechanical ventilation;
- 5 - Non-invasive mechanical ventilation (NIV) or high-flow oxygen;
- 4 - Hospitalized, requiring oxygen by mask or nasal prongs;
- 3 - Hospitalization without oxygen supplementation;
- 2 - Discharged from hospital either to home with supplemental oxygen OR to inpatient rehabilitation/skilled nursing facility (+/- supplemental oxygen);
- 1 - Discharged to home without supplemental oxygen

When calculating Ventilator Free days, reintubations or re-hospitalizations or death occurring in the first 28 days should result in zero ascribed to time off the ventilator prior to reintubation

When calculating days of hospitalization, re-hospitalization or death occurring in the first 28 days should result in zero ascribed to time out of the hospital prior to readmission.

When determining days of supplemental oxygen use and need for supplemental oxygen, the patient will only be considered to no longer need supplemental oxygen if a room air saturation is  $\geq 90\%$  after five minutes of rest.

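### Section 7.2 does not say how death counts when hospital stay and ventilation time are analysed as times to event, so the arm with more early deaths can look better

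*Combined protocol and SAP*

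**What the plan says.** Section 2.5 lists duration of hospitalization, duration of ventilation and ventilator-free days as secondary endpoints. Section 7.2 groups them with 30-day survival as time-to-event endpoints: "duration of hospitalization, duration of ventilation and ventilator free days, will be compared between treatment arms based on a log-rank test". It adds Kaplan-Meier medians by arm and Cox models adjusted for one covariate at a time. It does not say what the event is, when a patient is censored, or whether death is an event, a censoring or a competing event.

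The rules that mention death are elsewhere:

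- **Ventilator-free days.** Section 2.5: "reintubations or death within 28 days will result in zero ascribed time off ventilator prior to reintubation". Section 8.2: "When calculating Ventilator Free days, reintubations or re-hospitalizations or death occurring in the first 28 days should result in zero". The two differ, because 8.2 adds re-hospitalization.
- **Days of hospitalization.** Section 8.2: "re-hospitalization or death occurring in the first 28 days should result in zero ascribed to time out of the hospital prior to readmission".
- **Duration of ventilation.** No rule in any section.

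Section 4.1 follows control patients "until time of death or hospital discharge, whichever occurs earlier". That is an observation period and does not say how death is coded.

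**The concern.** Cohort 1 is intubated patients and Section 1.3 cites high mortality, so death will often be what ends a stay or a period of ventilation. The planned methods then depend on a coding that the plan leaves open, and neither ordinary choice is satisfactory.

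- **Death ends the episode.** An early death is recorded as a short stay or short ventilation, so it reads like a fast recovery.
- **Death is censored.** Kaplan-Meier treats the dead as if they could still be discharged or extubated later. The median then describes a setting without deaths and does not show that fewer patients leave alive.

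The trial is open-label. A coding not fixed in advance could be chosen with the results in view, and the choice can change the direction of the comparison.

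**Working it through.** **Reading the rules.** The 8.2 hospital-day rule sets to zero the time out of hospital before a readmission. A patient who dies without ever leaving has no such time and no readmission. The stay could be read as ending at death (short), as filling the 28 days (no time out of hospital), or as not covered. The second reading removes the bias, but the text does not select it. For duration of ventilation there is no text to interpret.

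**Inputs for an illustration.** The plan gives no figure on this point to reproduce. Only the 24 etoposide and 8 control patients per cohort (Section 7.1) and the 28-day horizon (Section 8.2) come from the document. All hazards are assumptions. The hazard *r* of leaving alive is the same in both arms: 0.03/day for discharge, 0.05/day for extubation. The death hazard *d* varies.

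**Formulas.**

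- Median, death as event: ln 2 / (r + d)
- Kaplan-Meier median, death censored: ln 2 / r
- Out alive by Day 28: r/(r + d) × [1 − exp(−28(r + d))]
- Dead by Day 28: the same with d/(r + d) in front

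**Hospital stay, r = 0.03.** For control, d = 0.02:

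- Median with death as event: ln 2/0.05 = 13.9 days.
- Median with death censored: ln 2/0.03 = 23.1 days.
- Out alive: 0.6 × [1 − exp(−1.4)] = 45%.
- Dead: 0.4 × [1 − exp(−1.4)] = 30%.

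| d | Median, death as event | Median, death censored | Out alive by Day 28 | Dead by Day 28 |
|---|---|---|---|---|
| 0.02 | 13.9 | 23.1 | 45% | 30% |
| 0.03 | 11.6 | 23.1 | 41% | 41% |
| 0.04 | 9.9 | 23.1 | 37% | 49% |
| 0.06 | 7.7 | 23.1 | 31% | 61% |

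As deaths rise, the first median improves, the second does not move, and the proportion out alive falls.

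**Log-rank, 24 v 8, hospital stay.** 10,000 simulated trials per row, two-sided 0.05, Monte Carlo standard error at most 0.5 points. Cells are % significantly favouring etoposide / control.

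| Death hazard, etoposide v control | Death as event | Death censored | Deaths held as non-events to Day 28 |
|---|---|---|---|
| 0.06 v 0.02 | 23.1 / 0.2 | 1.9 / 3.8 | 0.2 / 12.5 |
| 0.04 v 0.02 | 9.5 / 1.0 | 1.7 / 3.8 | 0.5 / 7.6 |
| 0.03 v 0.02 | 4.5 / 1.9 | 1.6 / 3.9 | 0.9 / 5.7 |
| 0.02 v 0.02 | 1.8 / 4.4 | 1.5 / 4.0 | 1.6 / 3.9 |

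Repeat runs gave 22 to 24% in place of 23.1%. The error works in both directions. With 0.02 on etoposide and 0.04 on control, death as event favours control in 14.7% of trials and etoposide in 0.3% (3,000 trials). The equal-hazard rate for control is 4.4%.

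**Duration of ventilation, r = 0.05.** With d = 0.06 on etoposide and 0.02 on control, 52.0% and 24.5% die on the ventilator by Day 28. The same patients give these medians, etoposide v control:

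- Death censored: ln 2/0.05 = 13.9 days in both arms.
- Death as event: ln 2/0.11 = 6.3 v ln 2/0.07 = 9.9 days.
- Deaths held to Day 28: not reached v 17.2 days. The etoposide proportion extubated alive cannot exceed 0.05/0.11 = 45%.

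So one dataset can show no difference, an apparent benefit or an apparent harm. With death as event, log-rank falsely favours etoposide in about 16% of trials. With d = 0.02 on etoposide and 0.04 on control, it falsely favours control in 11 to 12%. With equal hazards of 0.02 it rejects in 5.8%, both directions together.

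**The case against.** The strongest reply is that nobody reads these endpoints alone. Section 2.5 makes 30-day survival the key secondary endpoint. Among the simulated stay trials that falsely favour etoposide, observed mortality is higher on etoposide in 98%, 96% and 92% (death hazards 0.06, 0.04 and 0.03). A false benefit with no visible excess of deaths is therefore rare: 23.1% × 2% = 0.5%, 9.5% × 4% = 0.4% and 4.5% × 8% = 0.4% of trials. This stands and limits the harm. It does not remove it. With 8 controls, survival is significantly worse in only 46%, 27% and 17% of those trials, counting discharged patients as alive to Day 28.

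The largest rates also need a tripled death hazard, which is nowhere in the documents. At 41% v 30% mortality the excess over equal hazards is 4.5 − 1.8 = 2.7 points. That stands too.

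A reader might infer more than the text supports:

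- **That the plan counts death as the end of the episode.** It states no coding. The control follow-up sentence in 4.1 sets an observation period only.
- **That the gap favours etoposide.** It favours whichever arm has more early deaths.
- **That ventilator-free days share the fault.** They already score death as zero. Their problem is different: they are a bounded count, for which log-rank is a poor fit.
- **That control survival is censored at discharge.** Section 4.1 also provides Day 30 and Day 60 assessments without limiting them to one arm, 4.5 refers to a Day 60 survival assessment, and Section 6 says "Mortality assessment (included on the 8 point scale) will also be recorded at Day 14 and 60". Together these favour survival follow-up after discharge.

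**Conclusion.** The gap is real and should be closed before analysis. Death has no stated role in the log-rank, Kaplan-Meier and Cox analyses of two secondary endpoints. For ventilation no rule exists, and for hospital stay the 8.2 rule is ambiguous when a patient dies without leaving. Because both ordinary codings mislead, asking the sponsor to choose one of them would not be enough.

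The size is conditional on assumed constant hazards, with equal rates of leaving alive in the two arms, and on death being coded as an event. It ranges from under 3 percentage points of extra false benefit at a modest mortality difference to about 20 points at a tripled death hazard. An error of up to about 15% against etoposide is possible if the drug halves the death hazard. The primary endpoint and the 30-day survival comparison are not affected.

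**What to change.** **In 7.2**

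- Define the events as discharge alive and extubation alive, to Day 28. Hold patients who die by Day 28 as non-events to Day 28 and compare by log-rank. Alternatively, use cumulative incidence with death as a competing event and Gray's test. With status known to Day 28, the two address the same comparison.
- Apply the extubation analysis to patients ventilated at baseline. Cover patients intubated later through ventilator-free days.
- Compare ventilator-free days (death = 0) by Wilcoxon rank-sum test.
- Report hazard ratios from the Cox models. The sentence now ends "with odds ratios and 95% confidence intervals reported. Changes in inflammatory markers".

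**In 8.2 and 2.5**

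- State that a patient who dies in hospital by Day 28 has no days out of hospital.
- Use one definition of ventilator-free days in both sections.

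This extends to stay and ventilation the principle already applied to ventilator-free days, that death earns no credit.

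**Cost.** A few sentences and slightly more programming, with no extra patients or visits. Readmission or reintubation after discharge may be recorded incompletely, since the Day 30 footnote in Section 6 reads "Information to be obtained as feasible, if patient has been discharged attempts will be made to obtain the information". The number with unknown status should be reported by arm. With 8 controls per cohort the estimates stay imprecise under any method.
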